5.0 Study Procedures

Patient Focus Groups: For the formative & usability patient group (or individual interviews), after providing online consent, individuals will meet for a 1.5 hour conversation via Zoom, during which they will either provide formative feedback on the Memento approach and on new text messages & the usability of the prototype Memento system. Focus groups/interviews will be audiotaped. Participants will receive \$50 in an Amazon gift card at the end of each group/interview.

Healthcare Provider Focus Groups: For usability groups with healthcare providers (or individual interviews), after providing online consent, individuals will meet for a 1.5 hour conversation via Zoom, during which they will either provide formative feedback on the prototype Memento system, including how it might fit into clinical workflows, or usability feedback on its functioning. Focus groups will be audiotaped.

Participants will receive \$75 Amazon gift card at the end of the group.

Patient 6-week pre-post evaluation: After signing the online consent, participants will complete baseline assessments, pill regimen (including medication name, dosing, retail or mail-order pharmacy, the preferred time for pill reminders, refill due date, and how long they have been on HTN meds), and demographic data in the online Qualtrics platform. Participants will receive \$20 Amazon gift card for completion of baseline assessments. We will describe how to measure their arm with a tape measure (which we will have sent to them in advance) so that we can send them a correct size BP cuff. After taking the measurement, a new BP cuff (clinically- validated, blue-tooth enabled, Omron 5) will be delivered to each participant. Staff will meet again with participant (face-to-face or via zoom or phone) to guide them in getting baseline BP. The participant will be asked to sit quietly in a chair with their feet on the floor for several minutes, then measure their BP and pulse. Staff will record numbers. After another 5 minutes, the process will be repeated, yielding 2 BP readings, which will be averaged. Afterward, the participant will begin receiving SMS texts from the provider platform.

During the 6-week study period, patient participants will receive several types of text messages: daily interactive pill reminders, educational, motivational, spiritual/stress-supportive. Individuals that are 'new starts,' i.e. have been prescribed HTN meds within the last 8 weeks, will receive additional texts to support their implementation and persistence with their HTN med regimen. Study staff will monitor backend data to

determine if any patient participants are not opening their text messages or if a patient has missed pills 2 out of 7 days, which Dr.[name] has advised us is a clinically-significant pill lapse. In such instances, study staff will reach out to patients to see if they need support to help them with engagement.

At 6 weeks, patient participants will receive a phone call and text informing them it is time to re-take baseline assessments as well as to participate in end-of-study focus group (or individual interview). At the end of the study, participants will be invited to participate in a zoom focus group with up to 10 other participants or an individual interview (zoom or phone) to provide feedback on the Memento system.

After re-taking baselines and participating in the end-of-study focus group/interview, pre-post participants will be emailed a link for \$130 Amazon gift card.

6.0 Reporting of Adverse Events or Unanticipated Problems involving Risk to Participants or Others

We consider the risks to participants in both the patient and the healthcare provider focus groups to be minimal, i.e. there is a minor risk that other members of the patient focus group will know that a given participant is taking HTN medications. We will be clear in consenting patients that such a risk exists. There is a small risk of the time demand of the focus group will feel burdensome. We will make clear in informed consents for patients and for providers that they may end their participation at any time if the time demand becomes a problem.

Additionally, there is a risk to pre-post evaluation participants that someone will see their text messages and realize that the participant is taking HTN meds. In the pre-post informed consent, we will advise participants to delete any texts that they do not wish others to see. We will inform participants that state-of-the-art and HIPAA-compliant security protections are in place for any data in transit from the platform to their phone, but that there is still a risk to data in transit or privacy loss due to someone reading their text messages or breach of confidentiality due to data in transit or data storage. We will advise participants uncomfortable with those risks not to participate in the study. We will also outline in the informed consent measures that the team will take to protect their data.

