9.0. Outcome Measures

HTN med adherence will be assessed by the Adherence to Refills and Medication Scale (ARMS), a well-validated self-report measure used widely in studies with minority patients and/or those with low literacy (Buis et al., 2019; Kripalani et al., 2009; McNaughton et al., 2014). We will also use Segeral et al. (2010) 3-item adherence measure, as in our prior research (Pagan-Ortiz et al., 2019). Validated self-report measures correlate with clinical outcomes and are desirable to use in research with African American patients, who may resist providing bio-specimens due to historical mistrust (Ewing et al., 2019, Stirratt et al., 2015). Lastly, electronic pill bottles are cumbersome, expensive, and often ineffective for promoting and tracking adherence (Choudhry et al., 2017; Volpp et al., 2017).

Secondary: Adherence self-efficacy will be assessed with the HTN med adherence self-efficacy scale (MASES) (Ogedegbe et al. 2003). HTN knowledge will be assessed using the NHLBI HTN Knowledge Scale (Carter-Edwards et al., 2002). Stress burden will be assessed using Perceived Stress Scale (Cohen et al., 1983). **Exploratory:** BP will be measured at baseline and 6 weeks. **Primary Hypothesis:** Participants will show greater HTN med adherence at 6 wks compared to baseline.

Secondary Hypothesis: Participants will show greater HTN adherence self-efficacy, greater HTN knowledge, and lower stress burden at 6 wks compared to baseline. **Exploratory Hypothesis:** Participants will show a decrease in systolic BP at 6 wks compared to baseline. **Data analyses:** We will conduct one-tailed paired t-tests at the .05 level for primary and exploratory hypotheses and McNemar's chi square for secondary hypotheses. Data from our Phase 1 evaluation of short-term effectiveness will be used to determine the sample size necessary for an adequately-powered Phase 2 RCT.

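### The adherence baseline appears to be taken before cuff sizing, delivery and a second staff contact, so any adherence change before the first text, in either direction, enters the primary contrast

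*Protocol*

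**What the plan says.** Protocol section 5.0 (patient 6-week pre-post evaluation) gives the steps in order.

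- "After signing the online consent, participants will complete baseline assessments, pill regimen" and demographic data, all online in Qualtrics.
- Staff explain how to measure the arm, "so that we can send them a correct size BP cuff".
- "After taking the measurement, a new BP cuff" is delivered.
- "Staff will meet again with participant (face-to-face or via zoom or phone) to guide them in getting baseline BP", taken as the mean of two readings.
- "Afterward, the participant will begin receiving SMS texts from the provider platform".

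The same section places the repeat of the baseline assessments at 6 weeks, without naming the event from which the weeks are counted. It sets no time limit between any of these steps.

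Protocol section 9.0 states the primary hypothesis: "Participants will show greater HTN med adherence at 6 wks compared to baseline". The SAP repeats it. Both documents test it with a one-tailed paired t-test at the .05 level. Neither has a term for time between questionnaire and first text.

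Two other places describe baseline differently. Section 4.0 (Enrollment) counts the cuff reading among the online baseline assessments, and section 7.0 (Compensation and Costs) gives blood pressure as its example of what the baseline payment is for.

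**The concern.** In a single-arm study the baseline score is the only comparator. If it is taken one cuff shipment and one appointment before the intervention starts, the paired difference spans two periods: one before any text and one with texts. The plan attributes the whole difference to the text system. During the first period participants receive a home blood pressure monitor and use it with staff guidance, and neither is the text system. Adherence may move for these or other reasons, or may not move at all.

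The result matters beyond this pilot, because both documents say that Phase 1 data will be used to size the Phase 2 RCT. The undefined start of the six weeks adds a second uncertainty: participants may differ in how long they have received texts when they are reassessed.

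**Working it through.** The documents give no sample size, SD, effect size or gap length for the pre-post evaluation, so there is no figure to reproduce. The check is of the sequence, followed by illustrations on assumed inputs.

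**1. Is the adherence scale in the first step?** Section 5.0 does not name it there. But participants repeat the baseline assessments at 6 weeks, and the primary hypothesis compares adherence at 6 weeks with baseline. It is a sound inference that the scale belongs to the online baseline. The Protocol and SAP differ on which adherence scale is used; the timing point is the same for either.

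**2. Is a gap built in?** Yes, on section 5.0 as written. The cuff is sent only after the arm is measured, baseline blood pressure needs the cuff, and the texts follow that reading.

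**3. What does the paired difference contain?** Let Y0 be the score at the questionnaire, Y1 the score just before the first text (not measured under the plan) and Y6 the score at week 6, with higher meaning better adherence.

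Y6 − Y0 = (Y6 − Y1) + (Y1 − Y0)

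The second bracket is change before any text. Elapsed time alone adds nothing: if adherence is stable over the gap, that bracket averages zero.

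**4. Timing, with an assumed gap of g weeks.** If week 6 is counted from the first text, the untreated share is g/(6 + g). If it is counted from the questionnaire, text exposure is 6 − g weeks.

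| g (assumed) | Share before texts, clock from first text | Weeks of texts, clock from questionnaire |
|---|---|---|
| 1 | 1/7 = 14% | 5 |
| 2 | 2/8 = 25% | 4 |
| 3 | 3/9 = 33% | 3 |

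These are shares of calendar time, not of bias.

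**5. Effect on the test, with assumed drift and N.** Suppose the texts do nothing and mean adherence shifts during the gap by d SDs of the paired difference. The rejection probability is that of a noncentral t with N − 1 degrees of freedom and noncentrality d√N exceeding the one-sided 5% critical value. For d = 0.1 and N = 30 the noncentrality is 0.1 × √30 = 0.55.

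| N (assumed) | d = −0.1 | d = 0 | d = +0.1 | d = +0.2 |
|---|---|---|---|---|
| 20 | 0.019 | 0.050 | 0.112 | 0.217 |
| 30 | 0.015 | 0.050 | 0.134 | 0.283 |
| 50 | 0.010 | 0.050 | 0.172 | 0.401 |

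Upward drift raises the false-positive rate, downward drift lowers it, and no drift leaves it at 5%.

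**6. Effect on Phase 2 sizing, assumed inputs.** Drift common to both arms cancels in an RCT. At equal SD, an observed 0.4 SD that contains +0.1 SD of drift would understate the required N by a factor of (0.4/0.3)² ≈ 1.8. With −0.1 SD of drift, the N based on 0.4 SD would be (0.5/0.4)² ≈ 1.6 times what is needed.

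**The case against.** The strongest reply is that nothing in the documents shows that adherence changes during the gap. Its length, its variation between people, and the size and sign of any drift are all unstated. The tape measure is sent in advance, which tends to shorten the gap. Sections 4.0 and 7.0 treat the cuff reading as part of one baseline package. Section 5.0 describes the six weeks as the period in which texts are received, which favours counting from the first text. And this is a feasibility study without a power calculation, whose uncontrolled design has larger limits than this one. Most of that stands, and it keeps the point small. It does not remove it: sections 4.0 and 7.0 blur the date of baseline without reversing the order in section 5.0, and a plan that neither caps nor records the interval cannot later show that it was harmless.

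A reader might infer several stronger things that the documents do not support.

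- **That untreated time is itself credited to the intervention.** Only a change during that time is.
- **That the bias favours the intervention.** The direction is unknown, and a clock starting at the questionnaire could dilute the effect.
- **That regression to the mean drives it.** Eligibility does not select on low adherence, so the support for this is weak.
- **That listing the regimen is an exposure in the gap.** It is part of the same Qualtrics step as the baseline.
- **That new starts, who "have been prescribed HTN meds within the last 8 weeks", make the problem worse for the primary test.** They may be changing on their own, but in the plan this status only triggers extra texts and no subgroup analysis is planned.
- **That exploratory blood pressure is affected in the same way.** Its baseline reading directly precedes the texts.

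**Conclusion.** The point holds as a modest, cheaply removed weakness. On section 5.0 as written, and on the inference that the adherence scale is among the online assessments, the primary baseline precedes the intervention by an interval that is neither limited nor recorded. Any adherence change in that interval is inseparable from change under the texts. The secondary questionnaires share this if they are completed in the same step.

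The magnitude cannot be derived from the documents. The gap lengths, drift values and sample sizes used above are assumptions that show how the result would respond. They do not estimate what will happen, and the bias is zero if adherence is stable before the first text.

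**What to change.** 1. Administer the adherence scale at the already planned baseline blood pressure contact, immediately before the first text, and name that score as the primary baseline in the Protocol and SAP.
2. Count the six weeks from the first text and say so in section 5.0.
3. Record the dates of the consent questionnaire and first text, and report the interval.
4. Reconcile sections 4.0, 5.0 and 7.0 so that baseline has one clear date for each measure.
5. If the consent-time score is also kept, report the consent-to-first-text change descriptively only. That interval includes enrolment, cuff receipt and repeat-testing effects, so it is not a control. No recall period is stated either, and a long one would make the two early scores overlap.

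The cost is a few protocol lines and, if both scores are kept, one short self-report scale given once more. No extra visit or staff is needed. The change removes only pre-text drift from the contrast; other uncontrolled pre-post changes, including continued ownership of the cuff, remain.

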2.0 Goals

We propose a digital adherence solution to help reduce HTN-related disparities among African Americans, called Memento.HTN, which is innovative in three key ways: 1) it is the first-ever linked digital provider platform and patient SMS text system for HTN medication adherence; 2) it is culturally-tailored for African Americans with HTN; and 3) it has unique monitoring functionality allowing providers to monitor individual patient adherence, support 'new start' patients, who are at increased risk for non-adherence, and to track group adherence rates by drug class, pill format, and patient demographics in order to inform clinical therapeutics. Requiring only minutes of staff or prescriber monitoring per day, the Memento system simplifies and facilitates provider delivery of adherence support. The provider platform sends patients interactive SMS pill reminders plus culturally-sensitive motivational, educational, spiritual/stress-supportive, and customizable texts, along with texts that target intentional non-adherence. Importantly, Memento allows 2-way communication between providers and patients, and automatically alerts providers when a patient is having clinically-significant pill lapses.

Specific Aim 1: Develop an individually-tailored, culturally-sensitive digital health intervention comprised of a provider platform and linked patient SMS system to promote medication adherence in African Americans with HTN.

Specific Aim 2: Implement a 6-wk pilot to evaluate feasibility and short-term effectiveness for improving adherence.

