3.0 Inclusion/Exclusion Criteria

A detailed description of how subjects will be consented, study procedures, materials and potential risks for the study is provided below:

Inclusion/Exclusion Criteria for Patient usability and formative testing focus groups or individual interviews:

Inclusion: African American adults, age 18 and older, diagnosed with hypertension/high blood pressure, prescribed HTN meds, own a cellphone (basic or smart). Exclusion: Undergoing cancer treatment; pregnancy; end stage renal disease.

Inclusion/Exclusion Criteria for Patient 6 week pre-post evaluation: Inclusion: African American adults, age 18 and older, diagnosed with hypertension/high blood pressure, prescribed HTN meds, own a cellphone (basic or smart). Exclusion: Participation in other clinical research; undergoing cancer treatment; pregnancy; end stage renal disease.

Inclusion/Exclusion Criteria for Clinician usability and formative testing focus groups: Inclusion: Licensed clinicians (MD, PA, NP, RN, PharmD et al.) who work in primary care settings and prescribe anti-hypertensive medication treatment to adult patients with primary hypertension. Exclusion: Participation in other health services research.

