### **Analysis plan:**

**Measures: Primary:** HTN med adherence will be assessed by the Adherence to Refills and Medication Scale (ARMS), a well-validated self-report measure used widely in studies with minority patients and/or those with low literacy (Buis et al., 2019; Kripalani et al., 2009; McNaughton et al., 2014). We will also use Segeral et al. (2010) 3-item adherence measure, as in our prior research (Pagan-Ortiz et al., 2019). (NB: The team revised the adherence measure approach to use a single measure, namely the Wilson et al. (2016) Self-Report Medication Adherence scale.) **Secondary:** Adherence self-efficacy will be assessed with the HTN med adherence self-efficacy scale (MASES) new (Ogedegbe et al. 2003). Stress burden will be assessed using Perceived Stress Scale (Cohen et al., 1983). HTN knowledge will be assessed using the NHLBI HTN Knowledge Scale (Carter-Edwards et al., 2002). **Primary Hypothesis:** Participants will show greater HTN med adherence at 6 wks compared to baseline. **Secondary Hypothesis:** Participants will show greater HTN adherence self-efficacy, greater HTN knowledge, and lower stress burden at 6 wks compared to baseline.

**Data analyses:** We will conduct one-tailed paired t-tests at the .05 level for primary hypotheses. Data from our Phase 1 evaluation of short-term effectiveness will be used to determine the sample size necessary for an adequately-powered Phase 2 RCT.

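### Does pooling recently started patients with established ones undermine the exploratory systolic BP comparison?

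*Protocol*

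**What the plan says.** **Eligibility.** For the pre-post evaluation, Protocol 3.0 requires patients to be "diagnosed with hypertension/high blood pressure, prescribed HTN meds, own a cellphone (basic or smart). Exclusion: Participation in other clinical research". It sets no minimum time on treatment.

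**New starts.** Section 5.0 gives them extra content: "Individuals that are 'new starts,' i.e. have been prescribed HTN meds within the last 8 weeks, will receive additional texts". Section 2.0 explains the interest in this group. The platform is meant to "support 'new start' patients, who are at increased risk for non-adherence".

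**Data.** The baseline regimen questions in 5.0 include "refill due date, and how long they have been on HTN meds".

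**Analysis.** Protocol 9.0 labels BP exploratory and predicts: "Participants will show a decrease in systolic BP at 6 wks compared to baseline". The test is stated as: "We will conduct one-tailed paired t-tests at the .05 level for primary and exploratory hypotheses". No analysis in 9.0, 10.0 or the SAP uses time on treatment. The SAP lists no BP outcome and confines its t-tests to the primary hypotheses: "We will conduct one-tailed paired t-tests at the .05 level for primary hypotheses".

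**Purpose.** Specific Aim 2 in 2.0 is to "Implement a 6-wk pilot to evaluate feasibility and short-term effectiveness for improving adherence". Section 10.0 says that the pilot's size does not come from a power calculation.

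**The concern.** A patient prescribed a drug a few weeks before baseline may not yet have reached its full effect on BP. In one group with no control, any fall still to come counts toward the 6-week change, and the one-tailed test looks in exactly that direction. The Protocol admits such patients, defines them with an 8-week cut-off and records the variable that identifies them, yet plans a single pooled comparison.

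A reader of the pooled result could not tell whether the fall sat in a few recent starters or across the cohort. A significant decrease might then be taken as support for the programme when part of it came from ordinary drug initiation.

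**Working it through.** **1. Inputs.** The documents supply only the test: paired, one-tailed, alpha 0.05. They give no number of participants, SD of BP change, share of new starts or residual fall, so there is no plan figure to reproduce. Everything below is an assumption: n = 30, SD of change s = 12 mmHg, new-start share p = 10-20%, residual fall d = 2-4 mmHg, programme effect zero.

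**2. Effect of a residual fall on the pooled test.** The shift in the mean is p × d. The SD of the mixture is sqrt(s² + p(1−p)d²). The noncentrality is p·d·sqrt(n)/SD, and the rejection probability comes from the noncentral t with 29 degrees of freedom (critical value 1.699).

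Worked case, p = 0.2 and d = 4: the shift is 0.8 mmHg; SD = sqrt(144 + 0.16 × 16) = 12.11; noncentrality = 0.8 × 5.477/12.11 = 0.362; rejection probability 0.098.

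| Share | Change in new starts | Shift in pooled fall (mmHg) | P(significant decrease) |
|---|---|---|---|
| 0 | none | 0 | 0.050 |
| 10% | fall of 2 | 0.2 | 0.060 |
| 10% | fall of 4 | 0.4 | 0.071 |
| 20% | fall of 2 | 0.4 | 0.071 |
| 20% | fall of 4 | 0.8 | 0.098 |
| 20% | fall of 8 | 1.6 | 0.170 |
| 10% | rise of 4 | −0.4 | 0.034 |
| 20% | rise of 4 | −0.8 | 0.023 |

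**3. Direction.** The last two rows matter as much as the others. Section 2.0 singles out new starts for their risk of non-adherence, and 5.0 gives them texts to help them carry out and persist with treatment. If some lapse between baseline and 6 weeks, their BP could rise and the test would reject less often than 5%. The documents do not say which way the net effect goes.

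**4. Comparison with the general single-arm limitation.** Suppose everyone's BP falls by 2 mmHg for reasons unrelated to the programme, such as regression to the mean or familiarity with the cuff. With s = 12, the noncentrality is 2 × sqrt(n)/12:

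- all 30 participants: 0.913, rejection probability 0.226
- 27 established patients only: 0.866, rejection probability 0.211
- 24 established patients only: 0.816, rejection probability 0.197

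Setting the new starts aside leaves this almost untouched. Against it, a 2-4 mmHg residual fall adds 1 to 5 percentage points to the nominal 5%.

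**5. What a split by time on treatment would show.** The 95% half-width for a mean is t(0.975, n−1) × 12/sqrt(n):

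- all 30: 2.045 × 12/sqrt(30) = 4.48 mmHg
- 27 and 24 established patients: 4.75 and 5.07 mmHg
- 6 and 3 new starts: 12.59 and 29.81 mmHg

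For the difference between groups, t(0.975, 28) × 12 × sqrt(1/a + 1/b) gives 14.96 mmHg for 3 v 27 and 11.22 mmHg for 6 v 24. The effect in question is 2-4 mmHg.

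**6. What the split would mean.** The two groups differ in time on treatment and also in the texts they receive (5.0). By the reasoning in 2.0, new starts may also have more room to improve adherence. A larger fall in new starts could therefore be drug initiation, the extra texts, or the programme working as intended. The split cannot separate these.

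**The case for a change.** The factual side stands. No minimum time on treatment is required, duration is collected, and no planned analysis uses it. A residual fall, if there is one, would act in the direction tested. Pre-specifying a descriptive split costs a few sentences and no new data, and it would prevent a grouping being chosen after the results are seen.

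The size could also be larger than the table shows. With n = 20-50, a share of 10-50%, a residual fall of 3-10 mmHg and SD 10-15 mmHg, the shift runs from 0.3 to 5.0 mmHg and the rejection probability from about 6% to 93%. A middle case (n = 30, 25%, 6 mmHg) gives 13-19%.

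So wide a range shows that the answer is set by the assumptions. The high end needs half the cohort to be new starts with a 10 mmHg fall still to come, and no figure in the documents supports either. The 8-week cut-off is a rule for sending texts and has no stated link to when BP settles. Because duration is recorded at baseline in any case, a descriptive table remains possible whether or not the plan names it. What survives is a reasonable preference for an extra table.

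**Conclusion.** The concern does not hold. The pooled BP comparison is an exploratory result in an uncontrolled feasibility pilot, and the documents draw no conclusion from it that the new starts could distort. They predict a decrease but do not attribute it to the programme. Aim 2 ties short-term effectiveness to adherence, and it is that evaluation which 9.0 feeds into Phase 2 sizing. No text plans to size Phase 2 on pooled BP change.

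Under the assumed n = 30, SD 12 mmHg and 10-20% new starts, the rejection probability is 6-10% for a 2-4 mmHg residual fall, 3.4-2.3% for a 4 mmHg rise, and 5% if no new starts enrol or their BP has settled. A split could neither confirm nor exclude the supposed fall, and no BP estimate from this design could be attributed to the programme with or without it.

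Protocol 9.0 tests BP and the SAP omits it. That difference is a separate matter; if the SAP's omission governs, the present question does not arise. The adherence outcome is not affected by any of this.
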